## Background and Rationale

An estimated 6.5 million adults in the U.S. have heart failure (HF) with an estimated cost of >\$30 billion annually and projections show that the prevalence will increase 46% by 2030, because of population aging. One- and five-year fatality rates after HF hospitalization are exceptionally high at 22% & 42%. HF is characterized by poor quality of life due to a trajectory of worsening symptoms until death, but HF is amenable to management and prevention of symptoms. When symptoms occur, it is an indicator that hemodynamic measures are out of normal range, which requires intervention before symptoms accelerate into a patient crisis requiring emergent medical intervention. The most common HF symptoms also serve as warnings for impending crisis: chest pain, dyspnea, edema, fatigue, orthopnea, and anxiety/fear.

The amount of support available from providers to manage daily patient symptoms and complications is far beyond what is feasible during episodic primary care provider visits. Self-care patient behaviors are well known to improve HF outcomes; however, self-care is underutilized and underappreciated while pharmacological interventions are seen as more important by patients, clinicians and healthcare systems.

Recommended self-care behaviors are: accurate and timely symptom perception, daily management and ongoing preventive maintenance to include behaviors such as smoking cessation, maintenance of normal weight, regular physical activity, reducing dietary sodium, decreasing alcohol use, maintaining a healthy diet and cholesterol, monitoring blood pressure (BP), and blood glucose. Other prevention actions include annual dental exams, flu shots, health screenings and check-ups. The complex needs of these patients require a new vision and paradigm for delivery of health care services, such as an Mobile Health (mHealth) management model. mHealth technologies such as blue-tooth enabled BP, heart rate, weight, and pulse oximetry (POx) remote monitoring permit sharing of immediate real-time biometric data and video messages with providers & delivery of instantaneous feedback to patients before symptom crises.

mHealth interventions have been studied worldwide in >30 low-and middle-income countries. Recent meta-analyses and systematic reviews agree mHealth monitoring is generally effective in reducing HF hospitalization and short term mortality. Research is more limited and often equivocal but found somewhat effective in improving quality of life, medication adherence, cardiac lifestyle behaviors and disease management, and sometimes patient satisfaction. Most studies used hospitalizations and mortality as primary outcomes and *gaps in knowledge remain* with important patient-centered outcomes, such as self-care, symptom management, functional capacity, psychological distress, and caregiver burden. Additionally,

Study Title: Innovative Care of Older Adults with Chronic Heart Failure (I-COACH): A Comparative Effectiveness Clinical Trial  
PI (researcher): [name], RD  
Institution: University of Arkansas for Medical Sciences  
Funding: PCORI Grant

most studies did not stratify outcomes according to demographic variables or engage samples that were sufficiently racially/ethnically diverse.

mHealth technologies have established efficacy in the care of patients with HF, yet there is a decisional dilemma because HC systems, providers and payers do not know which care model should be used for a particular patient profile according to severity of HF, co-occurring multi-morbidities, or other patient characteristics or living situations, etc. Prevailing gaps in knowledge remain: Which patients will a mHealth model work better than the traditional provider-directed model for management of HF? Considering patient-centered outcomes, which model improves outcomes important to patients, such as function, symptom control, distress, quality of life, and caregiver burden?

## Specific Aims and Hypotheses

### Aim 1.

The principle aim of our proposed clinical trial is whether an enhanced *mHealth care management model* with connected health technology used in partnership with the healthcare system team, an older person with heart failure (HF), and their caregiver are more effective than a *provider directed management model* using non-connected home equipment kits. Self-care of HF, quality of life and quality care are represented by multiple outcome measures that are important to patients, caregivers and healthcare (HC) systems. Specifically,

**Aim 1a. Patient-centered outcome measures:** We hypothesize that the mHealth model will increase measures from baseline to 3- and 6-month for the primary outcome of self-care management of HF compared to the provider-directed model. Further, we hypothesize that the mHealth model will increase measures from baseline to 3- and 6-month for secondary outcomes of Self-efficacy to manage symptoms, medications, & treatments; self-care confidence; physical function, sleep, social roles, (Promis 43v2.1 Health profile); heart failure knowledge; satisfaction with care; quality of life; informational support and equipment usability (3 and 6 months), while decreasing health distress, anxiety, depression, fatigue, and pain compared to the provider-directed model.

**Aim 1b. Caregiver outcome measures:** We hypothesize that the mHealth model will reduce caregiver burden, while increasing caregiver health compared to the provider-directed model from baseline to 6-months.

**Aim 1c. Health system outcome measures:** We hypothesize that the mHealth model will reduce hospital admissions, 1-month readmissions, emergency department

Study Title: Innovative Care of Older Adults with Chronic Heart Failure (I-COACH): A Comparative Effectiveness Clinical Trial  
PI (researcher): [name], RD  
Institution: University of Arkansas for Medical Sciences  
Funding: PCORI Grant

visits, and 6-month mortality of HF participants while increasing satisfaction with care, compared to the provider-directed model.

### **Aim 2.**

We aim to explore associations of outcome measures with certain patient characteristics to determine which patients benefit the most from each care model, considering important patient-centered characteristics such as function, HF severity, rurality, and other demographic characteristics; and considering location of caregivers, and HC system outcomes such as emergency department visits and readmissions.

### **Aim 3.**

We aim to explore whether changes in self-efficacy, HF knowledge, and/or skills mediate the effect of self-care management.

## **Study Design and Procedures**

This will be a single-blinded comparative effectiveness randomized controlled trial conducted in a real-world setting. Subjects with HF and their caregivers (dyads) will be recruited and randomly assigned to one of two study arms:

- a provider-directed management model (with home monitoring equipment), a standard care-plus, OR
- an enhanced-mHealth care management model (with connected monitoring equipment).

Both groups will receive HF guideline-directed usual care, defined by the American Heart Association and College of Cardiology HF Guidelines with widely demonstrated effectiveness and have the same opportunity for education, nutrition counseling, nurse management, and HC provider access. This is usual care at UAMS.

Recruitment: Research participants will be recruited consecutively from the UAMS Medical Center. The project director will receive a daily list from UAMS bioinformatics core via UAMS secure/encrypted email of patients admitted to the hospital with a primary or secondary diagnosis of heart failure. Patients will be visited by the research team when they are stable and likely the day of discharge from the hospital (that way, likely the family/caregiver will be here as well). At that time, information will be given to the patient (and family/caregiver if present) about the study. If they would like to, we will obtain consent from both the patient and the caregiver if agreeable. Alternatively, they can think and talk about whether they want to participate and we will follow up after return home.

See section on participants and human subject protection for more details on

Study Title: Innovative Care of Older Adults with Chronic Heart Failure (I-COACH): A Comparative Effectiveness Clinical Trial  
PI (researcher): [name], RD  
Institution: University of Arkansas for Medical Sciences  
Funding: PCORI Grant

recruitment & consent.

The randomization will be generated using a computer algorithm using random permuted blocks (of differing size) to ensure balance over time in the numbers allocated to intervention groups and to avoid study staff anticipating the next treatment allocation. Randomization will be centrally generated by Co-I [name] and study staff who allocate interventions will be blinded to both the sequence and size of the blocks.

Participants will be randomized then they will complete baseline measures (self-reported survey measures, see Table 1.). Because all participants & caregivers will participate in the same recruitment procedures, measure timelines, and will receive monitoring equipment, participants will be blinded to their assigned group and will not be informed of which is the active intervention group. Both groups will receive standard education provided by the hospital and clinic providers, in addition the study staff will emphasize portions of the standard education provided regarding *emergency situations that require immediate action from the patient and/or caregiver such as; hypertension crisis, stroke signs and symptoms, and signs and symptoms of heart attack.*

**The provider-directed management model** is the current standard of care in the treatment of patients with HF including guideline-based HF care and a fee-for-service payment model in which the number of services and procedures that are provided are billed. Patients are typically scheduled for provider visits at a periodic interval rather than on patient needs, preferences, or circumstances. Care delivery is based on convenience of provider and sometimes on priority-based queues, that is If patients are having problems, they typically call the providers office or set up an appointment to visit the clinic weekdays and get priority scheduled. If problems occur at a different time, they frequently go to the emergency department (ED) at a local hospital or UAMS.

Caregiver burden is substantial in this model considering the patients' problem solving, care, and transportation needs. Our previous research confirmed both the traditional call/wait approach and ED alternative as usual means of provider communications. However, in this study, we are supplementing standard care by providing and training each patient in the use of an analog kit: (not internet connected) weight scale, blood pressure cuff, pulse oximeter, and a Log for recording their vital sign measures. Patients will be trained on the equipment and told to obtain a reading of weight, BP, and POx saturation every morning when they arise. Participants will make appointments, receive consultations, case-management, and resolve problems through in-person appointments or telephone communications as usually scheduled during the 6-month study follow-up.

Study Title: Innovative Care of Older Adults with Chronic Heart Failure (I-COACH): A Comparative Effectiveness Clinical Trial

PI (researcher): [name], RD

Institution: University of Arkansas for Medical Sciences

Funding: PCORI Grant

Subjects will be instructed to record their daily readings on a paper log provided by the research team. These monitoring devices will not transmit readings to a centralized

location and no one will be alerted to out-of-range readings or compliance with taking daily vital sign measures. At the front page of the log, normal ranges will be described with brief instructions about what participants/caregivers should do if their readings are out-of-range. These instructions will be developed with guidance from physicians/providers in the cardiology department. Per protocol, participants will be instructed to telephone the provider's office or the standard "on-call" line for further consultation and evaluation as needed. The number of provider visits will be collected using the electronic medical record and patient self-report). Patients will be encouraged to bring their vital sign measure logs to their provider appointments. Logs will be collected at the completion of their participation in the study. The log data will be recorded and saved for further data analysis.

**The mHealth care management model.** We will provide each patient randomized to this group with a weight scale, blood pressure cuff, & pulse oximeter (POx) kit connected to a Bluetooth-paired Android Health Tablet over the 6 months. This will allow real-time collection and monitoring of patient's vital sign measures, instantly accessible 24 hours a day, every day, by both patients and their clinicians, via a wireless gateway that transmits readings to a secure cloud-based clinician portal. The clinician portal will be monitored by the hospital's call center where registered nurses (RNs) will be specially trained to triage these patients according to physician/provider and study team-developed protocols.

Patients will be trained on the equipment and obtain a reading of weight, BP, and symptom survey every morning when they arise. A POx saturation reading will be obtained as needed. We used identical procedures in our pilot study and reported high patient daily adherence (85%) and call center accuracy (90%). Patients have the option to receive patient-centered education, nutrition counseling, nurse & medication management, and problem-based medical visits through live audio and video connected technology in their home. Diagnostic testing and some problems, if needed, will necessitate a visit to a local laboratory, regional UAMS clinic or main campus as usual. Caregivers will be encouraged to attend sessions or telehealth appointments from any location virtually. We will work with the providers, case managers, and our hospital system to train for telehealth visits as well as coding and billing.

Vital sign readings will be sent to the secure cloud-based software. Patients will be encouraged to take their vital signs daily. If the readings are out-of-range, the Registered Nurse (RN) Call Center will be automatically alerted via an email message. Protocols were developed by the medical providers as to acceptable and unacceptable

Study Title: Innovative Care of Older Adults with Chronic Heart Failure (I-COACH): A Comparative Effectiveness Clinical Trial  
PI (researcher): [name], RD  
Institution: University of Arkansas for Medical Sciences  
Funding: PCORI Grant

vital sign ranges/readings and actions. (We did this with the pilot study, and the procedure worked well). If within normal range, no intervention would be needed, and readings will be saved for future data analysis. This is considered a “green light”, that is no alert is triggered and no intervention is needed.

If readings are missed or trending out of range, or out of range now, the call center RN will follow the provider/study team developed protocol or algorithm for “yellow light” “orange light” or “red light”, in order of severity. The call center will monitor patients Monday-Friday 7-4pm as per the provider developed protocol. Patients will be instructed on what to do outside of those hours.

A “yellow light” alert means that the readings may begin to trend close to abnormal (too high or too low), or that the participant forgot to take the readings for that day. These patients will be flagged for follow-up. Yellow light follow up: RN call center reviews the new readings and if the trend has not continued, then no action will be taken. If the participant remembered to take his readings and they are within ranges set, no action will be taken. Participants will be encouraged to take readings daily but will not receive a call until they have multiple missed readings per provider developed protocol.

If the additional readings are “out of range” per protocol, then this is an “orange light” the RN call center nurse will telephone the participant and follow protocol. 1) for a missed readings: “inquired as to why they have been missing readings and ask the patient to take a reading now” if ok, no action will be taken and this encounter will be recorded.

If vital sign readings are abnormal, they will first check (per orange-light protocol) that the patient took the readings properly and that they took their medications that morning as usual before readings were taken. The RN will direct the participant to retake the vital signs after sitting for 15-30 minutes (per national guidelines), inquire if they have taken blood pressure/diuretic medication yet that day, and how they are feeling. Per yellow and orange-light protocol, if the preceding has not been done and readings are retaken and are normal, no further action will be taken. The encounter will be recorded by the call center RN. The Call Center will also direct the patient to follow protocols prescribed to them by their cardiology provider, such as the diuretic protocol for fluid retention/weight gain.

If the readings continue to trend out of range, this is considered an “orange light” and the provider/clinic will be notified by the call center RN of the information collected and vital signs and information recorded in EPIC and will be handed off to the provider to follow up as needed for medical care, this will occur M-F 7 am to 4 pm. During triage of an “orange light,” the Call Center will also direct the patient to follow protocols that are prescribed to them by their cardiology provider, such as the diuretic protocol for fluid retention/weight gain.

Study Title: Innovative Care of Older Adults with Chronic Heart Failure (I-COACH): A Comparative Effectiveness Clinical Trial  
PI (researcher): [name], RD  
Institution: University of Arkansas for Medical Sciences  
Funding: PCORI Grant

At that time, the participant's treatment plan may be altered by the provider to include increased vital sign tele-monitoring for that day, a change in medications, a video telemedicine home or in person office visit, or instructions to report to the emergency department for immediate evaluation and treatment if needed. The study team will not interfere with medical treatment and will not determine medical treatment. They will instruct the participant to follow prescribed protocols from their provider.

A "red light" is considered severe symptoms and/or critically abnormal vital signs. These patients are instructed at enrollment in the study *about emergencies that require immediate action (call 911 or go to the local emergency department) without waiting for a call from the call center, such as hypertension crisis, stroke signs and symptoms, and signs and symptoms of a heart attack.*

The call center will follow up on red alerts to make sure the participant followed standard education previously provided regarding emergencies and reeducate them and their caregiver as needed. As with all triage calls, this will be documented in the medical record.

If a yellow, or orange light occurs, and the participant does not answer the phone, the caregiver will be called. The caregiver will be instructed to make contact with the participant to return a call to the call center for instructions. If participant and caregiver are not available, a message will be left about the readings with instructions to telephone the call center number as soon as possible. A second call to the home and caregiver will be done this day if a return call is not received and same protocol will be followed as above. If no answer and no return call, this procedure will be followed per call center triage protocol.

mHealth participants will be told they can contact the call center RN for problems or concerns using the tablet or telephone and these will be triaged by RN call-center per protocol. Daily vital sign measures, recommendations, and responses will be transmitted, provider visits counted, tabulated and saved for analyses.

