### **Outcome Measures and Measurement Procedures**

Measurement instruments are included in Table 1 (next page) and grouped for the patient, caregiver, and system measures, specific aim addressed and type of outcome measure.

After screening to determine eligibility and fully informed consent process is followed and obtained, participants and caregivers will be randomized and asked to complete baseline assessments. Participants in both groups will be allowed to take assessment

Study Title: Innovative Care of Older Adults with Chronic Heart Failure (I-COACH): A Comparative Effectiveness Clinical Trial  
PI (researcher): [name], RD  
Institution: University of Arkansas for Medical Sciences  
Funding: PCORI Grant

questionnaires home to fill out within 1 week (+/- 1 week). The Research Assistant (RA) will travel to the participants' home, will be available by phone, or will arrange a convenient time before or after a closely timed provider appointment to complete the measures and train on use of the equipment. We will offer these convenience techniques at baseline, 3- and for the final 6-month follow-up measures.

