## **Data Analysis**

Data will be examined for completeness, outliers, and normality. Frequencies and percentages will be generated for screen failure reasons, for randomized participants, reasons for dropout and missing data. Descriptive statistics will be generated by intervention assignment and overall at 3 and 6 months. Baseline patient, caregiver, and system level characteristics will be compared according to intervention assignment to assess the success of the randomization; if there are imbalances, then consideration will be given to including the specific characteristic as a covariate to adjust intervention group comparisons. Continuous baseline variables will be compared using two-sample t-tests or nonparametric Wilcoxon rank sum & categorical variables will be compared using chi-square or Fisher's exact test.

Study Title: Innovative Care of Older Adults with Chronic Heart Failure (I-COACH): A

Comparative Effectiveness Clinical Trial

PI (researcher): [name], RD

Institution: University of Arkansas for Medical Sciences

Funding: PCORI Grant

For the Primary Outcome (Self-Care of Heart Failure Index, management subscale, Aim 1), we plan to compare arms in terms of change from baseline using a repeated measures mixed model analysis of covariance (ANCOVA) with an interaction between time and adjusting for baseline subscale score and other covariates such as age, race, education, and rurality. To address correlation arising from repeated measurements on the same subject over time, a random subject effect will be included in the model. For the primary endpoint, we will compare intervention effect at 3 months and at 6 months using contrasts (model-based t-tests) at a significance level of 0.025 (Bonferroni adjustment of alpha level of 0.05 for 2 comparisons). We will also use multiple imputation methods to address missing data (see below). Since scores  $> 70$  on the standardized scale have been used to indicate adequacy of self-care using a similar approach to the above, we will also analyze data as a binary endpoint in a repeated measures logistic model based on a generalized linear model framework.

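### The self-report baseline follows randomization and need not precede kit or training, so allocation can affect the baseline self-care score in the primary model

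*Combined protocol and SAP*

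**What the plan says.** **Order.** Study Design and Procedures states: "Participants will be randomized then they will complete baseline measures". Outcome Measures and Measurement Procedures says the same of the period after consent: "participants and caregivers will be randomized and asked to complete baseline assessments".

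**Timing and contacts.** Both arms may take "questionnaires home to fill out within 1 week (+/- 1 week"). The event that starts this window is not named. The research assistant may visit the home, help by telephone, or meet around a "provider appointment to complete the measures and train on use of the equipment". The order of the two tasks within a contact is not fixed.

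**What patients receive.** The provider-directed arm is supplemented by "providing and training each patient in the use of an analog kit", with a paper log. The mHealth arm receives a "kit connected to a Bluetooth-paired Android Health Tablet over the 6 months".

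**Masking.** The plan says that "participants will be blinded to their assigned group and will not be informed of which is the active intervention group".

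**Use of the baseline.** Under Data Analysis, "we plan to compare arms in terms of change from baseline using a repeated measures mixed model analysis of covariance (ANCOVA"). The baseline subscale score is also a covariate, and the arms are contrasted at 3 and at 6 months, each at 0.025. Baseline self-care score, depression and self-care confidence are listed as moderators. The mediation models adjust for baseline mediator and baseline outcome.

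**The concern.** A baseline covariate improves a randomized comparison because allocation cannot have influenced it. Here that is not assured. A patient could answer the Self-Care of HF Index after seeing, or being trained on, either a paper-log kit or a connected tablet kit. The questionnaire asks about the behaviour that both kits are meant to support.

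The masking statement does not close this route. It withholds which arm is the active one, but it does not hide what the patient has been given.

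Both arms receive equipment, training and the same standard education, so a shift common to both arms cancels. Only a difference between arms matters. If there is one, the primary model does not remove it, because the affected score is itself the adjustment variable. The self-report moderators and the mediator baselines have the same weakness. Age, race, rurality and items taken from the medical record do not.

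**Working it through.** **1. Is there a safeguard?** The two sections on order agree, so this is not a drafting slip. The masking statement concerns knowledge of the active arm. Concealment of the sequence and block sizes acts before allocation. Neither requires the baseline to precede kit or training.

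**2. Form of the bias.** With baseline slope b, the adjusted contrast is

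(difference in follow-up means) − b × (difference in baseline means).

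Suppose allocation adds d to the mHealth-minus-control baseline difference.

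- Nothing carried to follow-up: bias = −b × d. Because baseline is a covariate, this is the same for change scores and follow-up scores.
- A reporting shift f, not a real effect, remains at follow-up: bias = f − b × d.

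**3. Inputs.** The documents give 400 patients, up to 10% deaths by six months, and 0.025 per contrast (0.05/2). They give no SD, slope, effect size or power, so there is no sponsor figure to reproduce. Assumed: equal allocation, SD 20, slope 0.5 (range 0.3 to 0.7), true effect 6 points, and d of 1 to 3 points. Then n = 200 × 0.9 = 180 per arm. Each contrast is treated as a two-sample ANCOVA with two-sided critical value 2.241.

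**4. Shift at baseline only, slope 0.5.** Residual SD = 20 × √(1 − 0.5²) = 17.32; SE = 17.32 × √(2/180) = 1.826.

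| mHealth rise d | Expected estimate | Power | Rejection if no true effect |
|---|---|---|---|
| 0 | 6.0 | 85% | 2.5% |
| 1 | 5.5 | 78% | 3.1% |
| 2 | 5.0 | 69% | 4.8% |
| 3 | 4.5 | 59% | 7.9% |

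The false rejections under a rise almost all favour control; a fall in the mHealth baseline would favour mHealth. A simulation of 8,000 trials with d = 3 gave a mean estimate of 4.47 and power of 58%.

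Other slopes, with d = 3:

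- Slope 0.3: SE 2.011, bias −0.9, power 77% to 62%, null rejection 4.0%.
- Slope 0.7: SE 1.506, bias −2.1, power 96% to 64%, null rejection 19.9%.

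**5. Partial exposure.** These shifts are arm averages. If half the mHealth arm is exposed before baseline and each exposed patient shifts by 3 points, d = 1.5, bias = −0.75, power is 74% and null rejection 3.8%.

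**6. Shift that persists.** With no true effect and 3 points at both baseline and follow-up, the planned model is biased by 3 − 0.5 × 3 = +1.5 (rejection 7.9%), in favour of mHealth. An analysis of follow-up scores without baseline is biased by the full +3.0. Its SE is 20 × √(2/180) = 2.108 and its rejection 20.7%.

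**7. Would the planned baseline comparison reveal it?** With 200 per arm, SE = 20 × √(2/200) = 2.0. At two-sided 0.05, a shift of 1, 2 or 3 points is flagged 8%, 17% or 32% of the time. Chance alone gives a difference of 3 points or more in 13% of trials. The planned response to an imbalance is to consider adjustment, which the primary model already makes for this score.

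**The case against.** The other side has several fair points.

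- **Exposure is inferred.** The sentence on contacts names the measures before the training, and nothing schedules kit delivery ahead of the questionnaires. The missing-data paragraph also refers to data collection procedures that are not in the supplied text, so an ordering rule may exist elsewhere. This stands, and it limits the claim to a risk.
- **A difference between arms is a further step.** Nothing in the documents shows that brief contact with one kit moves the score more than contact with the other. This also stands.
- **The magnitudes are assumed.** They show sensitivity and do not estimate what will happen.
- **The direction is not fixed.** Patients keep the kits for 6 months, so a reporting shift could persist, and the bias would then differ in size and sign (step 6). This stands.

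A reader might infer that the baseline is contaminated, that patients are told their arm before answering, or that the primary result will be biased against mHealth. The documents support none of these. They plan no disclosure of which arm is active, they do not place training before the questionnaires, and they give no basis for a direction.

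The objection does not remove the stated order of randomization and baseline, or the lack of any rule in the supplied text holding back allocation, kit or training.

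**Conclusion.** The concern holds as an avoidable design risk. Allocation can affect the baseline self-care management score, the self-report moderators and the mediator baselines. Whether it does, by how much and in which direction cannot be known from the documents.

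For a shift of 1 to 3 points confined to baseline, with the assumed SD of 20 and slope of 0.5, the bias is 0.5 to 1.5 points against a true effect of 6. Over slopes 0.3 to 0.7, a 3-point shift gives 0.9 to 2.1 points. These figures assume arm-average shifts, equal allocation and 10% loss. The planned baseline comparison is too weak to give reassurance. The point should be fixed because it touches the primary model and prevention is simple; confidence is moderate because exposure is only possible.

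**What to change.** **Main change.** Amend Study Design and Procedures and Outcome Measures and Measurement Procedures to the order: consent, baseline, randomization, equipment training.

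**Fallback**, if this is unworkable on the day of discharge: complete at least the Self-Care of HF Index and the self-report moderator and mediator baselines before the allocation is disclosed and before any kit or training.

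**In either case**, record dates and times of baseline, randomization, kit delivery and training, and keep all randomized patients in the analysis.

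**Optional**, only where some baselines still follow kit contact: analyse the 3- and 6-month follow-up scores without the baseline score, keeping age, race, education and rurality. This removes baseline contamination only, not a reporting shift that persists at 3 and 6 months. Under the same assumptions its power is about 73% against 85%, calculated without covariates. It must use follow-up scores: an unadjusted change score carries the whole shift (6 − 3 = 3).

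**Cost.** The instruments and staff are unchanged.

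- By Table 1 times, the full patient baseline takes 90–118 minutes before allocation. The subset takes 8 + (3–5) + (10–20) + (15–20) + 20 + 5 = 61–78 minutes. Caregiver measures add 30 + (5–10) = 35–40 minutes if they are moved too. The plan already provides for home visits and for splitting the task within 2 days.
- Some patients will be lost before randomization instead of after it.
- Randomization must be obtained during or after the measurement contact.
- Under the fallback, kit and training may be delayed into the 1-month readmission window. The delay should be kept short and reported by arm.
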